7. STATISTICAL METHODS OF ANALYSIS

7.1 General Principles

The statistical analyses will be performed by [REDACTED], under the direction of the Sponsor, Actavis Laboratories UT, using SAS Version 9.3(or higher). All tables, figures, and listings will be produced in the landscape format.

In general, all data will be listed by treatment group, patient and visit/time point where appropriate. The summary tables will also be stratified by, or have columns corresponding to, treatment group.

All patients will be identified by their unique patient numbers. Data from the screen failures will not be included in tables, listings, or figures.

The total number of patients in the study group (N) under the stated population will be displayed in the header of summary tables.

Data will be summarized using descriptive statistics for continuous variables. Unless otherwise stated, descriptive statistics will include number of patients, mean, standard deviation, minimum, median, and maximum. The minimum and maximum statistics will be presented to the same number of decimal places as the original data. The mean and median will be presented to one more decimal place than the original data. The standard deviation will be presented to two more decimal places than the original data. The number of missing observations will be presented only if non-zero.

In summary tables of categorical variables, counts, and percentages will be used. The count [n] indicates the actual number of patients in a particular category, which should always be less than or equal to the total number of patients in the respective study group with known (non-missing) category [N]. Percentage will be obtained by: $\% = n/N*100$. Unless otherwise stated, all percentages will be expressed to one decimal place.

All statistical tests will be two-sided at a significance level of $\alpha = 0.05$, unless otherwise indicated. No adjustment will be made for multiplicity.

Relative days will be calculated relative to date of first dose of study medication. In general, relative days will be calculated as follows only when the full assessment date is known (i.e., partial dates will have missing relative days).

For assessment on or after the day of first dose of study drug:

Relative Day = Date of Assessment – Date of First Dose of study Drug+1.

For assessment before the day of first dose of study drug:

Relative Day = Date of Assessment – Date of First Dose of study Drug.

All dates will be displayed in DD/MMM/YYYY format.

7.2 Patient Disposition

The number of patients enrolled in the study, randomized to treatment, included in the Safety, PP, mITT populations, prematurely discontinued from the study (along with the reasons for discontinuation) will be calculated. The percentages will be based on the number of patients

randomized to each treatment group. Percentages for discontinuation reasons will be based on the sub-population of patients who discontinued from the study.

Number and percentage of patients enrolled by site will be tabulated for all enrolled patients, Safety, mITT, and PP populations.

7.3 Demographic and Baseline Characteristics

Demographic characteristics will include:

- age;
- gender;
- race;
- ethnicity;
- Rosacea history including time since diagnosis (years).

Baseline characteristics include:

- Baseline inflammatory lesion count;
- Baseline telangiectasia assessment;
- Vital signs: systolic and diastolic blood pressure, heart rate, respiratory rate, oral body temperature;
- Physical examination: height, weight;
- Medical history other than rosacea history.

Descriptive statistics will be presented for age (years), height, weight, body mass index (BMI), time since diagnosis (years), lesion count. Frequency counts and percentages will be presented for race, ethnicity, and baseline telangiectasia grade. Height will be reported in centimeters and weight in kilograms.

Age will be derived from Informed Consent Signed Date (INFCSD) and Date of Birth (DOB) as the number of whole years between those two dates.

Demographic and baseline/randomization characteristics will be evaluated for comparability across treatment groups in the following manner. Continuous variables (age, height, and weight) will be analyzed with an ANOVA with factors of treatment and investigational site. Overall p-value for the global null hypothesis of all groups being equal will be displayed. Categorical variables (gender, ethnicity, and race) will be analyzed with a Cochran-Mantel-Haenszel general association test, stratified by investigational site.

Separately, a categorical summary will be created for physical examination results and vital signs results (normal, abnormal not clinically significant, and abnormal clinically significant). Medical history other than rosacea history will be summarized by Medical Dictionary for the Drug Regulatory Activities (MedDRA) System Organ Class and Preferred Term. Baseline vital signs and physical examination will be listed.

These analyses will be performed for Safety, mITT, and PP populations.

All parameters reported during screening or baseline phase (including informed consent information, inclusion/exclusion criteria, randomization information, method of contraception, etc.) will be presented in the by-patient listings.

7.4 Protocol Deviations

Protocol deviations will be derived algorithmically. The following deviation categories will be derived:

1. Use of prohibited medication: use of any concomitant medication identified by the clinical review as critical and influencing the efficacy outcomes (major deviation).
2. Concomitant Medication – not critical: use of any other concomitant medication (minor deviation).
3. Diary accountability: subjects failing to return their diary at at least one scheduled visit (minor deviation).
4. Missed > 6 consecutive doses (major deviation).
5. IP compliance < 75% or > 125% (major deviation).
6. Dosing – Missed Doses(s): subjects who missed at least one dose, but do not fall under the previous two items (minor deviation).
7. IP Accountability: subjects who failed to return the IP at at least one scheduled visit (minor deviation).
8. Visit 4 out of window: subjects who attended Week 12 visit outside of \pm 4-day window (major deviation).

9. Failed to return to Visit 4: subjects who do not attend Visit 4 at all. This deviation will not apply to subjects who discontinued from study due to lack of treatment effect after at least 8 weeks of treatment (major deviation).
10. Inclusion/Exclusion criteria violated: subjects who were enrolled despite violating inclusion/exclusion criteria (major deviation).
11. Pregnancy: subjects with positive pregnancy test results at any time during the study or adverse event with preferred term "Pregnancy" or discontinuing from the study with reason "Pregnancy" (major deviation).
12. Urine Pregnancy Test not done: subject is female and of child-bearing potential, but UPT was not performed at Visits 2, 3, or 4 (minor deviation).
13. Facial lesion count not done at Visits 2 or 3 (minor deviation);
14. Facial lesion count not done at Visit 4 (major deviation);
15. IGE not done at Visits 2, 3, or 4 (minor deviation);
16. Sign and symptoms of local irritation not done at Visits 2, 3, or 4 (minor deviation).

Additional deviations may be reported by sites classified into deviation categories and graded as major or minor.

Protocol deviations will be summarized by deviation type and treatment group. This analysis will be performed for Safety, mITT, and PP populations.

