11.7.4 Visit 4/ (Day 84±4 days) /End of Treatment/ Early Discontinuation

The following procedures will be performed at Visit 4:

1. A urine pregnancy test will be conducted for all females of child-bearing potential.
2. All facial papules, pustules and nodules, located above the jaw line and extending to the hairline, will be counted (see Section 10.6.1).
3. The overall status of the patient's facial rosacea will be assessed using the IGE (see Section 10.6.2).

4. Patients will be evaluated for any signs and/or symptoms of facial irritation (see Section 10.5.6).
5. The occurrence of all AEs will be assessed and documented following procedures in Section 10.9.
6. The use of concomitant medications since the previous study visit will be documented for each patient. The use of moisturizer, including the type and how often it was used, will also be documented. (see Section 10.5.4).
7. The patient's compliance with the study protocol, including use and application of Investigational Product, will be assessed. The patient's diary will be collected and reviewed for completion.
8. Study drug compliance will be performed and the patient's used Investigational Product will be returned to the site.

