6.3 Per Protocol Population (PP Population)

The PP population includes all mITT patients who apply 75% to 125% of the scheduled applications of the assigned product for 12 weeks, do not miss more than 6 consecutive applications, return for the 12-week evaluation within +/- 4 days OR have discontinued from the study due to lack of treatment effect (after completing at least 8 weeks of compliant study medication use), and have no protocol major violations.

Patients who are discontinued prematurely from the study due to lack of treatment effect after completing at least 8 weeks of compliant study medication use and without major protocol violations will be included in the PP population as treatment failures (i.e., non-responders) even if they do not have Week 12 evaluation within the visit window or at all. An LOCF approach will be used for imputing missing lesion counts in these PP patients and they will be considered as failures in the IGE evaluations.

Patients discontinued prematurely for other reasons (including those who discontinue due to lack of treatment effect with less than 8 weeks of treatment) will be excluded from the PP population, but included in the mITT population, using LOCF.

Patients can be additionally excluded from the PP population due to non-compliance, if the Investigator's and Sponsor's review of their dosing times suggests a clinically meaningful departure from a twice-daily dosing pattern.

For the purpose of determining the PP status of the patient, a "major protocol violation" is any patient or investigator activity that could have possibly interfered with the therapeutic administration of the treatment or the precise evaluation of the treatment efficacy.

The PP population will be considered as definitive for testing the clinical equivalence and as supportive while testing the superiority.

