7.6.3 Exposure to Product

The patients will be instructed to use the diary to document all doses taken by checking the yes or no box for the appropriate date and am/pm time. The date(s) and reason for each dosing noncompliance must be recorded.

Compliance with scheduled application of IP will be determined from the patient's diary as $[Number\ of\ recorded\ applications] / [Planned\ number\ of\ applications] * 100\%$, where Planned number of applications is 168.

Number of missed doses will be calculated as follows. The number of doses missed in the dosing period (between the first and the last study drug application) will be taken directly from the CRF. Additionally, number of doses missed outside of the dosing period is the number of missed dosing times between the date and time (AM/PM) of the last dose and the date and time when the subject would have reached the required 168 doses (i.e. the date and time (AM/PM) of the first dose plus 84 days, inclusive)..

Patients who have more than 6 consecutive missed doses will be considered non-compliant and will be excluded from the PP population. For the dosing period >6 consecutive applications will be collected directly on the eCRF. Additionally, patients will be considered having >6 consecutive missed doses if after the dosing period patients missed more than 6

dosing times after their last dose and prior to the morning of Visit 4 date or the date and time (AM/PM) when they would have reached the required 168 doses, whichever occurs earlier. Patients can be additionally excluded from the PP population due to non-compliance, if the Investigator's and Sponsor's review of their dosing times suggests a clinically meaningful departure from a twice-daily dosing pattern.

Patients will be considered compliant if they apply at least 75% and not more than 125% of doses, with no more than 6 consecutive missed doses. The compliance will be analyzed using the descriptive statistics by treatment group. The proportion of compliant vs. non-compliant patients will be tabulated for each treatment.

Duration of exposure will be calculated as Date of last use of study medication – Date of first use of study medication + 1. Duration of exposure will be summarized descriptively by treatment group.

Compliance and duration of exposure will be summarized for the Safety and mITT populations.

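### SAP 7.4 and 7.6.3 do not carry through the SAP 6.3 rule that keeps late treatment failures in the per-protocol population

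*SAP*

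**What the plan says.** A late failure here means a patient discontinued for lack of treatment effect after at least 8 weeks of compliant use.

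**Inclusion.** SAP 6.3 puts late failures in PP as non-responders, "even if they do not have Week 12 evaluation within the visit window or at all", provided they have no major violation. SAP 7.5.2 gives them carried-forward lesion counts in the PP analysis, SAP 7.5.3 scores them as IGE failures there, and protocol 12.4.4 has the same inclusion rule. PP is the definitive set for equivalence.

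**Deviations.** SAP 7.4 derives deviations by algorithm. Item 9 (no Visit 4) carries an exemption: "This deviation will not apply to subjects who discontinued from study due to lack of treatment effect after at least 8 weeks of treatment". The other relevant items are graded major with none:
- item 4, "Missed > 6 consecutive doses (major deviation";
- item 5, "IP compliance < 75% or > 125% (major deviation";
- item 8, "Visit 4 out of window: subjects who attended Week 12 visit outside of" plus or minus 4 days;
- item 14, "Facial lesion count not done at Visit 4 (major deviation".

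**Dose counting.** SAP 7.6.3 fixes the planned applications at 168. It counts dosing times after the last dose as missed up to Visit 4 or the 168-dose date, whichever is earlier, and then states: "Patients who have more than 6 consecutive missed doses will be considered non-compliant and will be excluded from the PP population".

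**Visit naming.** The protocol section headed "Visit 4/ (Day 84±4 days) /End of Treatment/ Early Discontinuation" gives the early discontinuation visit and Visit 4 one set of procedures. Protocol 11.3.4 asks for these procedures at discontinuation only where possible.

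**The concern.** The exemption in item 9 deals with one consequence of stopping early, the absent Visit 4. Stopping early has other consequences: doses not taken, a final visit before the window, or no lesion count at Visit 4. The SAP treats these as non-compliance or major deviations. The patients whom 6.3 deliberately keeps can then be removed by 7.6.3, or flagged by 7.4 for the very facts that 6.3 says do not matter. Two programmers could build different PP sets from the same text.

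At stake is the treatment-failure branch of the definitive equivalence set. These are poor responders, identified after randomisation. If Test and Reference produce them at different rates, leaving them out hides part of a real difference, in both the lesion-count ratio and the IGE success difference. SAP Section 8 declares no changes from the protocol analyses, so nothing suggests that this narrowing is intended.

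**Working it through.** **Inputs.** Twice-daily dosing for 84 days (SAP 3.1); 168 planned applications, the limit of 6 consecutive misses and the end of the count (SAP 7.6.3); the 75% limit (SAP 6.3); Visit 4 window of Days 80-88 (Day 84 ± 4).

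**The plan's own figure.** 2 × 84 = 168, which reproduces.

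**Formulas.** Take a fully compliant patient with a morning first dose on Day 1 who stops at the end of Day D. Applications = 2D; doses missed to the 168-dose date = 168 − 2D; compliance = 2D/168.

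| Stop on Day | Applications | Missed to 168 | Compliance |
|---|---|---|---|
| 56 | 112 | 56 | 66.7% |
| 62 | 124 | 44 | 73.8% |
| 63 | 126 | 42 | 75.0% |
| 70 | 140 | 28 | 83.3% |
| 79 | 158 | 10 | 94.0% |
| 80 | 160 | 8 | 95.2% |
| 81 | 162 | 6 | 96.4% |

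The missed run exceeds 6 through Day 80. Compliance is below 75% through Day 62. An evening first dose lowers applications by one and moves these limits to Day 81 and Day 63.

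**Rules applied literally**

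| Situation | Item 4 / 7.6.3 | Item 5 | Item 8 | Item 14 |
|---|---|---|---|---|
| A. No Visit 4 recorded, or early discontinuation visit not counted as Visit 4 | Applies, stops through Day 80 | Applies, stops on Days 56-62 | No | Applies |
| B. Early discontinuation visit counted as Visit 4, on the day of stopping, lesions counted | No; applies if the visit is more than 6 dosing times after the last dose | Applies, stops on Days 56-62 | Applies before Day 80 | No |
| C. Drug stopped on Days 76-79, Visit 4 on Day 80 | No (at most 6 missed) | No | No | No |

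**Which of these reach PP.** The limit on consecutive misses and the 75% limit are PP criteria in 6.3, so items 4 and 5 exclude directly. Items 8 and 14 reach PP only if a major deviation in 7.4 is also a major violation in 6.3, and no sentence says so.

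**Repairing only items 4, 8 and 14.** Item 5 would still remove stops on Days 56-62. A patient stopped at Visit 3 on Days 56-60 lies wholly in that band (66.7% to 120/168 = 71.4%). Visit 3 is the only scheduled visit between Week 8 and the Week 12 window.

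**Possible size of bias (illustrative).** The documents give no failure rates. Assume 3% on Test and 1% on Reference, a 55% mean reduction in other patients on both products (the plan's figure for the reference), and a mean reduction v of 20% or 0% in failures.
- v = 20: Test 0.97 × 55 + 0.03 × 20 = 53.95; Reference 0.99 × 55 + 0.01 × 20 = 54.65; ratio 0.987.
- v = 0: Test 53.35; Reference 54.45; ratio 0.980.

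Dropping the failures returns the ratio to 1.00, which hides 0.013 to 0.020. For scale, take 55%, SD 47% (the plan's upper bound), 224 per arm and an observed ratio of 1. The standard error is 47/√224 = 3.14. With t about 1.648, g = (1.648 × 3.14/55)² = 0.0089. The Fieller lower limit is [1 − (1.648 × 3.14/55) × √(2 − 0.0089)]/(1 − 0.0089) ≈ 0.875, which leaves 0.075 above 0.80. With equal failure rates and equal outcomes in both arms, the shift is zero.

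**The case against.** The best defence is that 6.3 is explicit and specific, and that a general deviation list should not override it. SAP 7.4 says only that deviations are summarised, including within PP, and 6.3 has its own definition of a major violation. Item 8 speaks of the Week 12 visit, and a discontinuing unscheduled visit has its own name. Item 14 can be read as a count omitted at a Visit 4 that was attended; otherwise it cancels the exemption in item 9. Missed doses stop accruing at Visit 4, so a failure stopped and examined on the same day gains none if that visit is Visit 4. The supportive mITT equivalence analysis keeps these patients anyway.

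Much of this stands. A reader might infer that every failure stopped on Days 56-79 drops out of PP. The documents do not support that: items 8 and 14 are a conflict with 6.3 and not a settled exclusion, and situation C triggers nothing. Nor can it be said that PP will favour equivalence, since that needs unequal failure rates, which the documents do not give.

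The defence does not rescue the plan. If the early discontinuation visit is not Visit 4, the missed-dose count runs to the 168-dose date and 7.6.3 excludes the patient. If it is Visit 4, item 8 grades as major exactly what 6.3 says must not exclude. Neither reading helps the compliant failure stopped on Days 56-62.

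**Conclusion.** The concern holds in this form. SAP 7.4 and 7.6.3 do not implement the inclusion that 6.3, 7.5.2 and the protocol require.

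- **Directly excluded:** failures with no recorded Visit 4, or with an early discontinuation visit not counted as Visit 4, for stops through Day 80; failures whose Visit 4 comes more than 6 dosing times after the last dose; and fully compliant failures stopped on Days 56-62, through the fixed denominator.
- **Under conflicting rules:** other failures discontinued before Day 80, through item 8. Item 14 adds the same conflict where there is no Visit 4.
- **Unaffected:** a patient who stops drug on Days 76-79 and is seen on Day 80.

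The day limits assume full compliance and a morning first dose. The number of patients affected cannot be computed from the documents. The ratio shift of 0.013 to 0.020 rests wholly on assumed failure rates and outcomes; it is modest against 0.075. The rules should be corrected before unblinding because they decide membership of the definitive set.

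**What to change.** 1. In SAP 7.4, replace the exemption in item 9 with a common rule: items 8, 9 and 14 do not apply to patients discontinued for lack of treatment effect after at least 8 weeks of compliant treatment.
2. In SAP 7.6.3, for these patients, end the count of missed doses (item 4) at the date of the decision to discontinue, and take the planned applications for percent compliance (item 5) up to that same date.
3. State whether the early discontinuation visit counts as Visit 4.
4. State whether a major deviation in 7.4 determines PP status under 6.3.

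The cost is a few SAP sentences and a small change to the deviation and compliance programs. A few poor outcomes return to PP, as the protocol already intends.

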7.5 Efficacy Analyses

7.5.1 Center pooling

To eliminate potential effect of random fluctuations at small site on the primary endpoints small centers will be pooled. A study center will be pooled if it doesn't meet both of the following conditions:

- It has at least 10 patients in the PP population;
- It has at least one patient in each treatment group in the PP population.

The smallest center that does not meet the above requirements will be pooled with the next smallest center. The procedure will be repeated until all pooled centers meet the above two requirements.

Pooled center will be used in all the efficacy analyses.

7.5.2 Analyses of Primary Endpoint

At each visit, an Investigator will assess the patient's facial rosacea by counting the number of pustules, papules, and nodules. The number of pustules, papules, total number of inflammatory lesions (pustules and papules) and nodules will be reported on the CRF.

Missing Week 12 assessments will be imputed as follows. In the mITT analysis, if a patient discontinues the study prior to Week 12 or misses the Week 12 assessment for any other reason, the LOCF rule will be used to impute the number of lesions. In the PP analysis, if a patient discontinues the study prior to Week 12, due to lack of treatment effect, after at least 8 weeks of treatment, the LOCF rule will be used to impute the number of lesions. If a patient is missing the Week 12 assessment for any other reason, the patient will be excluded from the PP population.

The baseline lesion count will be defined as the results from the latest examination prior to the start of study drug therapy. For each post-baseline visit the change from Baseline and percent change from Baseline in the total number of inflammatory lesions will be calculated. The baseline value, timepoint value, change from baseline, and percent change from baseline at the timepoint will be analyzed using descriptive statistics and will be tabulated by site, visit, and treatment group.

7.5.2.1 Analysis of clinical equivalence of test and reference treatments

To show the clinical equivalence, estimates of mean percent change from Baseline in the inflammatory lesion count will be calculated for the Test and Reference treatment, and then the 90% CI for the mean ratio will be constructed using Fieller's method. Bioequivalence will be established if the 90% confidence interval for the ratio of Test/Reference means is contained within the interval [0.80, 1.25] for the PP population.

To this end, first an ANOVA model will be fit with percent change from Baseline in lesion count as outcome and treatment, center and treatment-by-center interaction, as factors on the data from Test and Reference treatments only (excluding Vehicle patients). If the treatment-by-center interaction factor is not significant at the 0.05 level, the model will be rerun without the interaction term. Treatment means and standard errors will be estimated from this model.

Then Fieller's formula will be applied; covariance between the treatment means will be assumed to be 0. See [Appendix 11.4](#) for complete description of the Fieller's formula.

A non-parametric rank based ANOVA will be considered when the data is highly skewed. The evaluation of skewness, (using SAS® PROC UNIVARIATE) will be performed using the residuals from ANOVA and if the skewness statistic is less than -2 or greater than +2, the analysis will be performed on the ranks of the percent change in the inflammatory lesion count values.

Analysis of bioequivalence will be performed both on the PP population and on the mITT population. The results on the PP population will be considered definitive and the results on the mITT population will be considered supportive.

